6.7 Data monitoring board

Not applicable.

7. STUDY MANAGEMENT

7.1 Monitoring

Before first patient enrolled into the study, a representative of AstraZeneca will visit the investigational study site to:

- Determine the adequacy of the facilities
- Discuss with the investigator(s) (and other personnel involved with the study) their responsibilities with regard to protocol adherence, and the responsibilities of AstraZeneca or its representatives. This will be documented in a Clinical Study Agreement between AstraZeneca and the investigator.
- Discuss the specific requirements of the genetic research with the investigator(s) (and other personnel involved with the study)

During the study, a monitor from AstraZeneca or company representing AstraZeneca will have regular contacts with the study site, including visits to:

- Provide information and support to the investigator(s)
- Confirm that facilities remain acceptable
- Confirm that the investigational team is adhering to the protocol, that data are being accurately recorded in the eCRFs, and that investigational product accountability checks are being performed
- Perform source data verification (a comparison of the data in the eCRFs with the patient's medical records at the hospital or practice, and other records relevant to the study). This will require direct access to all original records for each patient (e.g. clinic charts).
- Perform source verification of the genetic consent of participating patients and ensure that the investigational team is adhering to the specific requirements of this genetic research.

The monitor or another AstraZeneca representative will be available between visits if the investigator(s) or other staff at the centre need information and advice.

7.2 Audits and inspections

Authorised representatives of AstraZeneca, a regulatory authority, an Ethics Committee may visit the centre to perform audits or inspections, including source data verification. The purpose of an AstraZeneca audit or inspection is to systematically and independently examine all study-related activities and documents to determine whether these activities were conducted, and data were recorded, analysed, and accurately reported according to the protocol, Good Clinical Practice (GCP), guidelines of the International Conference on Harmonisation (ICH), and any applicable regulatory requirements. The investigator should contact AstraZeneca immediately if contacted by a regulatory agency about an inspection at his or her centre.

7.3 Training of staff

Prior to the study start regional meetings will be held with all investigators and/or other staff involved from each study centre and AstraZeneca representatives. During the meeting, participants will have an opportunity to discuss the procedures associated with the study, the requirements for collection of blood samples and the genetics part in accordance with [Appendix E](#). The importance of the informed consent process will be made clear.

Before the first patient is entered to the study the appropriate investigational staff will be trained by AstraZeneca personnel or delegates on how to use the WBDC system, laboratory related issues and all other necessary means which will be used in this study.

The principal investigator will maintain a record of all individuals involved in the study (medical, nursing and other staff). He or she will ensure that appropriate training relevant to the study is given to all of these staff, and that any new information of relevance to the performance of this study is forwarded to the staff involved.

7.4 Changes to the protocol

Study procedures will not be changed without the mutual agreement of the Co-ordinating Investigator and AstraZeneca/Bristol-Myers Squibb.

If it is necessary for the study protocol to be amended, the amendment and/or a new version of the study protocol must be notified to or approved by each Ethics Committee, and if applicable, also the local regulatory authority, before implementation. Local requirements must be followed.

If an administrative change is required, such a change must be notified to or approved by each Ethics Committee according to local requirements.

If a protocol amendment requires a change to a particular centre's Informed Consent Form, then AstraZeneca and the centre's Ethics Committee must be notified. Approval of the revised Informed Consent Form by AstraZeneca and by the Ethics Committee is required before the revised form is used.

AstraZeneca will distribute amendments and new versions of the protocol to each principal investigator(s), who in turn is responsible for the distribution of these documents to, and to the staff at his or her centre. The distribution of these documents to Ethics Committee and the regulatory authority will be handled according to local practice.

7.5 Study agreements

The principal investigator at each centre must comply with all the terms, conditions, and obligations of the Clinical Study Agreement for this study. In the event of any inconsistency between this Clinical Study Protocol and the Clinical Study Agreement, the Clinical Study Protocol shall prevail.

7.6 Study timetable and end of study

Before a patient's enrolment in the study and any study-related procedures are undertaken the following should be fulfilled:

- Signed Clinical Study Protocol and other agreements between AstraZeneca and the Principal Investigator/Study Site.
- Approval of the study by the Ethics Committee
- Approval of the study, if applicable, by the regulatory authority.

The planned overall timetable for the study is as follows:

First Patient In Q2 2008

Last Patient In Q1 2009

24-weeks double-blind treatment period:

Last Patient Last Visit Q2 2009

Long term double-blind extension period I:

Last Patient Last Visit Q4 2009

Data base lock Q1 2010

Long term double-blind extension period II

Last Patient Last Visit Q1 2011

Data base lock Q1 2011

End of study is defined as database lock, which is the time point after which no patients will be exposed to study related activities.

8. ETHICS

8.1 Ethics review

AstraZeneca will provide Ethics Committees and Principal Investigators with safety updates/reports according to local requirements.

The final study protocol, including the final version of the Informed Consent Form, must be approved or given a favourable opinion in writing by an Ethics Committee as appropriate. The investigator must submit written approval to AstraZeneca before he or she can enrol any patient into the study.

The Principal Investigator is responsible for informing the Ethics Committee of any amendment to the protocol in accordance with local requirements. In addition, the Ethics Committee must approve all advertising used to recruit patients for the study. The protocol must be re-approved by the Ethics Committee annually, as local regulations require.

Progress reports and notifications of serious and unexpected adverse drug reactions will be provided to the Ethics Committee according to local regulations and guidelines.

Where there is a genetic research, approval must be obtained for this genetic research and the associated genetic informed consent from the Ethics Committee. It must be clearly stated in the approval that this genetic research is approved. The investigator must submit written approval to AstraZeneca before any patient participates in this genetic research

8.2 Ethical conduct of the study

The study will be performed in accordance with ethical principles that have their origin in the Declaration of Helsinki and are consistent with ICH/Good Clinical Practice, applicable regulatory requirements and the AstraZeneca policy on Bioethics.

For studies including genetic analysis special precautions are taken as described in [appendix F](#).

8.3 Informed consent

The principal investigator(s) at each centre will ensure that the patient is given full and adequate oral and written information about the nature, purpose, possible risk and benefit of the study. Patients must also be notified that they are free to discontinue from the study at any time. The patient should be given the opportunity to ask questions and allowed time to consider the information provided.

The patient's signed and dated informed consent must be obtained before conducting any procedure specifically for the study, including the following:

- Withholding or discontinuation of treatment

- Collection of blood and urine samples
- Physical examination including ECG

The patient's signed and dated informed consent for study prolongation must be obtained before extending the active study treatment at visit 12.

The principal investigator(s) must store the original, signed Informed Consent Form. A copy of the signed Informed Consent Form must be given to the patient.

If modifications are made according to local requirements, the new version has to be approved by AstraZeneca.

8.4 Subject data protection

The Master Informed Consent Form will incorporate (or, in some cases, be accompanied by a separate document incorporating) wording that complies with relevant data protection and privacy legislation. Pursuant to this wording, patients will authorise the collection, use and disclosure of their study data by the Investigator and by those persons who need that information for the purposes of the study.

The Master Informed Consent Form will explain that study data will be stored in a computer database, maintaining confidentiality in accordance with national data legislation. All data computer processed by AstraZeneca and Bristol-Myers Squibb will be identified by E-code and study code.

The Master Informed Consent Form will also explain that for data verification purposes, authorised representatives of AstraZeneca, a regulatory authority, an Ethics Committee may require direct access to parts of the hospital or practice records relevant to the study, including patients' medical history.

All data protection and confidentiality principles, described in the main study protocol, are applicable to this genetic research.

Reference to participation in this genetic research should not be recorded into the patients' general medical records. All notes should be kept within the clinical study records.

Due to the exploratory nature of this genetic research, there will be no routine communication of results to patients. AstraZeneca and Bristol-Myers Squibb will not provide individual genotype results to patients, any insurance company, any employer, their family members, general physician or any other third party, unless required to do so by law.

Extra precautions are taken to preserve confidentiality and prevent genetic data being linked to the identity of the patient, however, it must be recognised that there are exceptional circumstances where individuals may see both genetic data and a patient's personal identifier, for example in the case of a medical emergency, when AstraZeneca Physicians and investigators might know the patients' identity and might have access to the genetic data, or during regulatory audit where designated authorities must be permitted access to the relevant files.

9.2 Procedures in case of medical emergency

The principal investigator(s) is responsible for ensuring that procedures and expertise are available to handle medical emergencies during the study. A medical emergency usually constitutes an SAE and should be reported as such, see section [4.7.1.1](#).

The treatment code may not be broken unless in an emergency situation when the appropriate management of the patient necessitates knowledge of the treatment allocation. In such an emergency, the Investigator will, if time and circumstances permit, contact the local AstraZeneca representative prior to breaking the treatment code. If the treatment code is broken, the date, time, and reason should be recorded and the Investigator should sign the record, see also section [3.6.2](#).

9.3 Procedures in case of overdose

An overdose is defined as the accidental or intentional ingestion of any dose of an investigational product that is considered both excessive and medically important. All occurrences of overdose must be reported as an SAE (see section [4.7.1.3](#)). If an overdose is suspected, monitoring of vital functions as well as treatment as appropriate should be performed.

9.4 Procedures in case of pregnancy

If a patient becomes pregnant, the investigational product should be stopped and the AstraZeneca representative should be informed. The pregnancy report module in the eCRF should be completed by the investigator and the AstraZeneca representative will forward the information to BMS using the same procedure as for SAE reporting. The outcome of each pregnancy will also be collected once this information is available.

Pregnancy itself is not regarded as an AE unless there is a suspicion that the investigational product under study may have interfered with the effectiveness of a contraceptive medication. However, the outcome of all pregnancies (spontaneous miscarriage, elective termination, normal birth or congenital abnormality) must be followed up and documented even if the patient was discontinued from the study.

All reports of congenital abnormalities/birth defects are SAEs. Spontaneous miscarriages should also be reported and handled as SAEs. Elective abortions without complications should not be handled as AEs. All pregnancies must be reported on the pregnancy module in the eCRF. All outcomes of pregnancy must be reported to AstraZeneca on the pregnancy outcomes report that will be available in the Investigator Study File

Appendix Date	

Appendix B
Additional Safety Information

FURTHER GUIDANCE ON THE DEFINITION OF A SERIOUS ADVERSE EVENT (SAE)

Life threatening

‘Life-threatening’ means that the subject was at immediate risk of death from the AE as it occurred or it is suspected that use or continued use of the product would result in the subject’s death. ‘Life-threatening’ does not mean that had an AE occurred in a more severe form it might have caused death (eg, hepatitis that resolved without hepatic failure).

Hospitalisation

Out-patient treatment in an emergency room is not in itself a serious AE, although the reasons for it may be (eg, bronchospasm, laryngeal oedema). Hospital admissions and/or surgical operations planned before or during a study are not considered AEs if the illness or disease existed before the subject was enrolled in the study, provided that it did not deteriorate in an unexpected way during the study.

Important medical event or medical intervention

Medical and scientific judgement should be exercised in deciding whether a case is serious in situations where important medical events may not be immediately life-threatening or result in death, hospitalisation, disability or incapacity but may jeopardize the subject or may require medical intervention to prevent one or more outcomes listed in the definition of serious. These should usually be considered as serious.

Simply stopping the suspect drug does not mean that it is an important medical event; medical judgement must be used.

Examples of such events are:

- Angioedema not severe enough to require intubation but requiring iv hydrocortisone treatment
- Hepatotoxicity caused by paracetamol (acetaminophen) overdose requiring treatment with N-acetylcysteine
- Intensive treatment in an emergency room or at home for allergic bronchospasm
- Blood dyscrasias (eg, neutropenia or anaemia requiring blood transfusion, etc) or convulsions that do not result in hospitalisation
- Development of drug dependency or drug abuse.

A GUIDE TO INTERPRETING THE CAUSALITY QUESTION

The following factors should be considered when deciding if there is a “reasonable possibility” that an AE may have been caused by the drug.

- Time Course. Exposure to suspect drug. Has the subject actually received the suspect drug? Did the AE occur in a reasonable temporal relationship to the administration of the suspect drug?
- Consistency with known drug profile. Was the AE consistent with the previous knowledge of the suspect drug (pharmacology and toxicology) or drugs of the same pharmacological class? OR could the AE be anticipated from its pharmacological properties?
- Dechallenge experience. Did the AE resolve or improve on stopping or reducing the dose of the suspect drug?
- No alternative cause. The AE cannot be reasonably explained by another aetiology such as the underlying disease, other drugs, other host or environmental factors.
- Rechallenge experience. Did the AE reoccur if the suspected drug was reintroduced after having been stopped? AstraZeneca would not normally recommend or support a rechallenge.
- Laboratory tests. A specific laboratory investigation (if performed) has confirmed the relationship?

A “reasonable possibility” could be considered to exist for an AE where one or more of these factors exist.

In contrast, there would not be a “reasonable possibility” of causality if none of the above criteria apply or where there is evidence of exposure and a reasonable time course but any dechallenge (if performed) is negative or ambiguous or there is another more likely cause of the AE.

- In difficult cases, other factors could be considered such as:
- Is this a recognised feature of overdose of the drug?
- Is there a known mechanism?

Ambiguous cases should be considered as being a “reasonable possibility” of a causal relationship unless further evidence becomes available to refute this. Causal relationship in cases where the disease under study has deteriorated due to lack of effect should be classified as no reasonable possibility.

Clinical Study Protocol: Appendix C

Drug Substance	Dapagliflozin
Study Code	D1690C00006
Appendix Edition Number	1.0

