3.3.3 Exclusion criteria

Any of the following is regarded as a criterion for exclusion from the study:

Exclusion criteria at randomization visit (visit 2):

1. Clinical diagnosis of type 1 diabetes, MODY or secondary diabetes mellitus (eg chronic pancreatitis, partial pancreatectomy).
2. Symptoms of poorly controlled diabetes that in judgement of the investigator would preclude participation in this trial including, but not limited to, marked polyuria and polydipsia with greater than 10% weight loss during the 3 months prior to enrolment.
3. Treatment with more than two additional OADs
4. History of diabetes insipidus

5. Use of inhaled insulin or injectable GLP-1 receptor agonists or DPP-4 inhibitors within 8 weeks of enrolment visit
6. Calculated Creatinine Clearance <50 ml/min/1.73m² (calculated by Cockcroft-Gault formula) or a measured serum creatinine value of >2 mg/dl (177 μ mol/l). Patients on concomitant metformin therapy will be excluded if serum creatinine ≥ 1.5 mg/dl (133 μ mol/l) for male subjects and ≥ 1.4 mg/dl (124 μ mol/l) for female subjects
7. Known condition of congenital renal glucosuria
8. Total bilirubin >34.2 μ mol/l, >2.0 mg/dl
9. Creatine kinase ≥ 3 xULN
10. Hemoglobin ≤ 10.0 g/dl (≤ 100 g/l) for men; hemoglobin ≤ 9.5 g/dl (≤ 95 g/l) for women
11. Thyroid-stimulating hormone (TSH) values outside normal range confirmed by abnormal T4 values
12. Positive serologic evidence of current infectious liver disease including patients being positive for Hepatitis B viral antibody IgM, Hepatitis B surface antigen and Hepatitis C virus antibody.
13. Any clinically significant abnormality identified on physical examination, ECG or laboratory tests, which in the judgement of the investigator would compromise the patients' safety or successful participation in the clinical study.
14. Significant cardiovascular history within the past 6 months prior to the screening visit, defined as: myocardial infarction, unstable angina pectoris, transient ischemic attack, unstable or previously undiagnosed arrhythmia, cardiac surgery or revascularization (coronary angioplasty or bypass grafts), or cerebrovascular accident
15. Pregnant or breastfeeding patients
16. Treatment with glucocorticoids equivalent to oral prednisolone >10 mg (betametasone >1.2 mg/dexametasone >1.5 mg/hydrocortisone >40 mg)/day within 30 days prior to enrolment; topical or inhaled corticosteroids are allowed
17. History of bariatric surgery

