4.7.1 Adverse events

4.7.1.1 Definitions

The definitions of adverse events (AEs) and serious adverse events (SAEs) are given below. It is of the utmost importance that all staff involved in the study are familiar with the content of this section. The principal investigator is responsible for ensuring this.

Adverse event

An adverse event is the development of an undesirable medical condition or the deterioration of a pre-existing medical condition following or during exposure to a pharmaceutical product, whether or not considered causally related to the product. An undesirable medical condition can be symptoms (e.g., nausea, chest pain), signs (e.g., tachycardia, enlarged liver) or the abnormal results of an investigation (e.g., laboratory findings, electrocardiogram). In clinical studies, an AE can include an undesirable medical condition occurring at any time, including run-in or washout periods, even if no study treatment has been administered.

Serious adverse event

A serious adverse event is an AE occurring during any study phase (i.e., run-in, treatment, washout, follow-up) and at any dose of the investigational product, comparator, or placebo that fulfils one or more of the following criteria:

- Results in death
- Is immediately life-threatening
- Requires in-patient hospitalisation or prolongation of existing hospitalisation
- Results in persistent or significant disability or incapacity
- Is a congenital abnormality or birth defect
- Is an important medical event that may jeopardise the patient or may require medical intervention to prevent one of the outcomes listed above.
- Cancer
- Overdose (defined as the accidental or intentional ingestion of any dose of the investigational product that is considered both excessive and medically important)

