4.7.5 Independent Adjudication Committee

4.7.5.1 Cardiovascular Clinical Event Committee (CCEC)

A Cardiovascular Clinical Event Committee (CCEC), blinded to the treatment of the subjects, will independently adjudicate certain cardiovascular adverse events, and they will operate in accordance with a dedicated Clinical Event Committee Charter/Manual of Operations: Dapagliflozin Program.

Events related to the following will be sent to the CCEC for adjudication:

Death including:

- (a) Cardiovascular Death
- (b) Non-cardiovascular Death

Myocardial Infarction (MI) including:

- (a) ECG and /or cardiac enzymes confirmed MI
- (b) Sudden death
- (c) PCI-related myocardial infarction
- (d) CABG-related myocardial infarction
- (e) MI diagnosed via pathologic criteria
- (f) Silent MI

Fatal and Non-fatal Stroke including:

- (a) Ischemic stroke
- (b) Hemorrhagic stroke

Serious Adverse Events of the following:

- (a) Heart failure
- (b) Cardiac arrhythmia
- (c) Unstable angina
- (d) Unplanned arterial revascularization (coronary, carotid and peripheral)
- (e) Cardiac arrest with successful resuscitation
- (f) Deep Vein Thrombosis and Pulmonary Emboli
- (g) Systemic non-stroke arterial embolism/thrombosis including systemic arterial occlusion
- (h) Non-traumatic amputation of the lower limb. Only events above the ankle will be considered for adjudication.

In order to provide the independent CCEC with appropriate and adequate information for adjudication of the listed events, please consult the Reference Manual, Dapagliflozin Cardiovascular Adjudication Reference Manual for Primary Investigators and Study Staff.

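### Appendix B exempts planned admissions for pre-existing disease unless the worsening was unexpected, a test that the adverse event definition in Section 4.7.1.1 does not contain

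*Protocol*

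**What the plan says.** Three parts of the protocol bear on this.

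- **Section 4.7.1.1 (Definitions).** An adverse event includes "the deterioration of a pre-existing medical condition following or during exposure to a pharmaceutical product, whether or not considered causally related to the product". Nothing is said about whether the deterioration was foreseeable. An adverse event that requires in-patient hospitalisation is serious, and planned admissions are not carved out. The section then refers the investigator to Appendix B for guidance on the definition of a serious adverse event, so the appendix is working guidance and not background.
- **Appendix B (Hospitalisation).** The rule covers admissions as well as operations, and reads in part: "surgical operations planned before or during a study are not considered AEs if the illness or disease existed before the subject was enrolled". It reaches any disease already present at that point, and only one proviso limits it: "provided that it did not deteriorate in an unexpected way during the study". The appendix does not define what makes a deterioration unexpected.
- **Section 4.7.5.1 (CCEC).** The cardiovascular committee adjudicates death, myocardial infarction and stroke under their own headings. A further group, including heart failure, arrhythmia, unstable angina, unplanned revascularisation and non-traumatic amputation above the ankle, is listed for adjudication as serious adverse events.

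**The concern.** Exempting an admission or operation is sound when the underlying condition is stable, because nothing has happened to the patient that could reflect treatment. Appendix B goes further. It keeps the exemption when the condition has worsened, provided that the worsening was of a kind that could be expected, and it applies this to admissions arranged after randomisation. Worsening after randomisation is what Section 4.7.1.1 sets out to capture.

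Patients with relevant pre-existing disease can be enrolled. Section 3.3.3 excludes "Significant cardiovascular history within the past 6 months prior to the screening visit" and heart failure of NYHA class III or IV or with an ejection fraction of 40% or less. Older arterial disease and NYHA class I or II heart failure are therefore not excluded by these criteria. Section 1.2 gives cardiovascular risk as the reason for adding extension period II. At stake are the completeness of serious adverse event reporting, its consistency across about 150 centres (Section 3.1), and, for a small set of events, whether they reach the cardiovascular committee.

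**Working it through.** No arithmetic applies. The protocol gives neither the number of patients with pre-existing cardiovascular disease nor a rate of planned admissions. The check is to take the possible situations one by one and read each under both passages.

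| Situation | Section 4.7.1.1 | Appendix B | Agree? |
|---|---|---|---|
| Procedure arranged before enrolment, condition stable | No new or worsened condition, so no adverse event | Exempt | Yes |
| Elective procedure arranged during the study, condition stable | No new or worsened condition, so no adverse event | Exempt | Yes |
| Known condition worsens unexpectedly, planned admission | Adverse event, serious by hospitalisation | Exemption lost | Yes |
| Known condition worsens as expected, planned admission | Adverse event, serious by hospitalisation | Admission is not an adverse event | **No** |
| Known condition worsens, emergency admission | Adverse event, serious by hospitalisation | Does not apply, because the admission was not planned | Yes |

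Only the fourth row conflicts. What separates it from the third row is the word about expectedness, which Section 4.7.1.1 does not use and Appendix B does not define.

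The adjudication list in Section 4.7.5.1 can then be read against that fourth row.

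- Death, myocardial infarction and stroke have their own headings and do not depend on the serious adverse event route. An acute infarction or stroke is also not a planned admission.
- Unstable angina, cardiac arrest, venous thromboembolism and arterial embolism are ordinarily acute, so an admission for them is seldom planned.
- Revascularisation is on the list only when unplanned. A scheduled one is outside adjudication whatever Appendix B says.
- Heart failure can lead to an arranged admission in an enrolled patient with NYHA class I or II disease.
- Amputation above the ankle can be a scheduled operation for arterial disease known at enrolment.

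The last two are the clearest cases in which an event could miss adjudication because Appendix B was followed.

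**The case against.** The strongest reply is that the passages can be read together. Appendix B exempts the admission or operation, and an admission is not itself a medical condition. It does not say that the underlying deterioration is not an adverse event. The deterioration can still be recorded under Section 4.7.1.1, and a clinically relevant aggravated examination finding under Section 4.7.1.2. It may also be serious by another criterion, such as persistent disability or an important medical event. This stands, and it narrows the point. It does not settle whether an expected worsening that led to a planned admission is serious by hospitalisation: Section 4.7.1.1 says yes, while Appendix B says the admission does not count.

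It can also be said that adjudication is governed by a charter and a reference manual that are not available here, so it cannot be asserted that such an event would never reach the committee. That stands too. The point is that the protocol's own route runs through serious adverse event status.

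A third objection is that the exemption should not simply be restricted to procedures planned before enrolment, because an elective operation scheduled during the study for stable disease is not an adverse event under Section 4.7.1.1 either. That is correct, and the fix respects it.

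A reader might go further and infer that expected cardiovascular deterioration as a whole is removed from serious event counts and from adjudication, or that the rule biases the cardiovascular comparison towards no difference. The documents support neither. Only planned admissions and operations are exempted, and most of the adjudication list is untouched. The same rule applies in every arm under blinded investigators (Section 3.6.1), and nothing in the protocol shows a differential loss. Nor is there a basis for putting a percentage on lost events or on lost precision: no rates are given, and Section 6.4.4 plans only descriptive safety summaries.

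**Conclusion.** The point holds in a narrow form. Section 4.7.1.1 and Appendix B give different answers for one situation: a pre-existing condition that worsens as expected during the study and leads to a planned admission or operation. Which answer is applied rests on an undefined judgement by each investigator. The plausible consequences are some under-reporting of serious adverse events, inconsistency between sites, and in a few cases, such as an arranged heart-failure admission or a scheduled above-ankle amputation, an event that does not reach the cardiovascular committee. The size cannot be derived from the documents. No efficacy endpoint, significance level or sample size is affected. The conclusion assumes that investigators follow Appendix B as written and that the adjudication charter and manual, which are not available, do not already close the gap.

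**What to change.** Reconcile the two passages with two edits to the protocol text.

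1. In Appendix B, delete the unexpectedness qualifier, so that the exemption applies only if the pre-existing condition did not deteriorate during the study. Keep the exemption for elective procedures in stable disease, whether arranged before or during the study.
2. In Appendix B or Section 4.7.5.1, state that an event on the committee's list that arises from worsening of a pre-existing disease and meets a seriousness criterion is reported and sent for adjudication, even if the admission was planned.

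The cost is a wording change, a few more serious adverse event reports and a few more adjudication packages.
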